STUDY PROTOCOL WITH STATISTICAL PLAN

FORM DATED FROM NOV. 22nd 2023

PI: [name]

**MODULATION OF THE ELECTROMAGNETIC PULSE ON THE ORAL
BIOFILM OF INDUCED GINGIVITIS AND MUCOSITIS: PROTEOMIC AND
MICROBIAL EFFECTS**

GUARULHOS

2023

[name]

**MODULATION OF THE ELECTROMAGNETIC PULSE ON THE ORAL
BIOFILM OF INDUCED GINGIVITIS AND MUCOSITIS: PROTEOMIC AND
MICROBIAL EFFECTS**

Research project to the Research Ethics Committee of Univeritas-UNG University

Area of concentration: Implantology

RESPONSIBLE: [name]. [name]

ABSTRACT

As in natural teeth, bacterial colonization of the implant surface can trigger a reversible inflammatory process in the peri-implant soft tissue-defined mucositis. However, differences in the organization of peri-implant tissues may combat the progression of lesions associated with bacterial biofilm, resulting in a broader inflammatory infiltrate compared to periodontal tissues. Some previous studies have used electromagnetic pulses (PEMF-pulse electromagnetic fields) to modulate bacterial biofilm. Thus, the objective of this study will be to evaluate the host response pattern (proteomics, microbiome, and clinical) during the induction and progression of experimental gingivitis and mucositis in humans with the action of the electromagnetic pulse. Forty systemically healthy individuals will be included, who must present the need for two implant-supported restorations adjacent to the teeth. Individuals will receive oral hygiene instruction and professional prophylaxis fortnightly, 30 days before implant installation. The implants will be installed in time -60 days. After 60 days, at baseline, the healing abutment will be installed on the two implants, one conventional and the other with an electromagnetic pulse. At the same time, everyone will receive acetate plates to protect the selected areas (tooth and implants) during brushing, to be used for 21 days. Clinical periodontal parameters, microbiological (supragingival and subgingival biofilm), and immunological (crevicular fluid) collections will be obtained at 0, 3, 7, 14, 21, 42, and 60 days. The results will be evaluated for normality using the D'Agostino test. Then, parametric or non-parametric tests will be applied to compare the means/medians obtained between the gingivitis and mucositis groups in the different periods of the study.

Keywords: Oral Surgery, Dental Implant, Microbiome, Proteome, Gingivitis, Mucositis.

SUMMARY

	Page

1. INTRODUCTION

Prosthetic rehabilitation by means of osseointegrated implants is currently a well-established method in dentistry, offering excellent aesthetic and functional results with high predictability. However, it is known that numerous implants are lost early or late (Zitzmann; Berglundh, 2008; Shibli et al. 2015). Among the main causes of these losses are: the patient's systemic health condition, smoking, bone quality, the experience of the dental surgeon, inadequate prosthetic planning, occlusal overload, parafunctional activity, and bacterial infection at the time of or after surgery (Zitzmann; Berglundh, 2008).

As with natural teeth, bacterial colonization of the implant surface can trigger a reversible inflammatory process in the peri-implant soft tissue (Salvi et al., 2012), called mucositis. When not identified and treated, this inflammatory process can intensify and progress apically, leading to clinical signs very similar to those of periodontitis. Peri-implantitis leads to loss of bone support followed by remodeling of the supporting periodontium during the healing process (American Academy of Periodontology, 2013).

The main risk indicators for mucositis involvement, according to Lindhe and Meyle (2008), are: poor oral hygiene, history of periodontitis, smoking, diabetes, alcohol consumption and genetic factors, with the first three mentioned having a higher degree of evidence.

It is known that the interface between soft tissue and osseointegrated implant has several similarities with the tissue around natural teeth, but some differences should be considered. The absence of the periodontal ligament, the main one, can limit the peri-implant blood supply, especially on the surface immediately adjacent to the implant surface (Carranza et al., 2012) Histologically, the collagen fibers around the implants are oriented in parallel without insertion on their surface, while in the teeth the collagen fibers are perpendicular and insert into the cementum (Hanisch et al., 1997).

The evaluation of the formation of dental bacterial biofilm on the surface of dental implants by scanning electron microscopy indicates that the formation patterns identified in implants are very similar to those observed in teeth (Lang et al., 2000).

In a clinical study, Zitzmann et al. (2001) demonstrated that the changes that occurred in the gingiva and peri-implant mucosa during the experimental period of biofilm accumulation induction did not present statistically significant differences,

which, for the authors, indicates that the host response to dental plaque or peri-implant is, in many aspects, comparable.

Although few, clinical studies that have compared the response of gingival and peri-implant tissues to biofilm formation through the analysis of clinical signs (plaque index, gingival bleeding index, and depth of probing and bleeding on probing) of the host response have reached very similar results (McKenna; Borzabadi-Farahani; Lynch, 2013; Tawse-Smith et al., 2012; Berglundh et al. 1992; Ericsson et al., 1992; Pontoriero et al., 1994; Zitzmann et al., 2001). However, differences in the organization of peri-implant tissue mean that combating the progression of lesions associated with bacterial plaque results in a broader inflammatory infiltrate, when compared to gingival tissue (Melo, 20019). As can be seen in the study by Salvi et al. (2012) who, in addition to the clinical signs, evaluated the crevicular gingival fluid of their sample and observed that the soft tissues around the implants developed a more intense inflammatory response during the experimental period of plaque accumulation, when compared to that of their gingival counterparts. Zitzmann et al. (2001) and Zitzmann et al. (2002) found similar results in their studies.

Recently, however, Albrektsson et al. (2014), suggested that the basic mechanism behind marginal bone loss around implants cannot be compared to that described for periodontal diseases, but rather, with a foreign body reaction. This assumption, based only on a few explanations from isolated cases, has been widely disseminated without being questioned.

Few studies evaluating the effects of biofilm formation around implants (McKenna, Borzabadi-Farahani, Lynch, 2013; Salvi et al., 2011; Zitzmann et al., 2001, 2000; Pontoriero et al., 1994) compared the peri-implant response to periodontal disease with bacterial biofilm accumulation (McKenna, et al., 2013; Salvi et al., 2011; Zitzmann et al., 2001; 2000; Tawse-Smith et al., 2001), but were inconclusive or did not analyze the host's immune response to this experimental model. However, studies evaluating the host's immune response to this colonization are still scarce and often inconclusive. Regardless of gingival health and subgingival microbiota, inflammatory cytokines produced within peri-implant tissues may be different from those present in periodontal tissues (Nowzari et al., 2012). Therefore, more specific studies correlating the microbiological findings to the analysis of cytokines and proteins around teeth and implants using the experimental gingivitis model should be performed.

In addition, previous studies using *pulse electromagnetic fields (PEMF)* in the modulation of bacterial biofilm have drawn attention (ZHOU et al. 2017). Although **PEMF** has been used more frequently to increase bone density and osseointegration (BUZZA et al. 2003; BARAK et al. 2016), recent advances in the miniaturization of the equipment have allowed the entire apparatus to be inserted into an implant healer (BARAK et al. 2016; BARAK et al. 2019).

Using this PEMF-emitting healer, our group evaluated the effect of the activated healer (PEMF+) on periodontal bacterial biofilm with 31 species in *an in vitro model* (Faveri et al. 2020). In this study, PEMF healers modulated the bacterial biofilm, reducing some bacterial species of the orange complex and increased one species of the blue complex (beneficial species). In the meantime, it would be very interesting to evaluate the effect of this technology during the induction of experimental mucositis, on the modulation of the biofilm and consequently the host reaction.

Therefore, there is a need to evaluate a greater number of markers around the periodontal and peri-implant fluids, as well as their correlation with the microorganisms present during biofilm maturation through the induction of experimental gingivitis/mucositis.

2. OBJECTIVE

To evaluate the host response pattern (proteomics, microbiome, and clinical) during induction and progression of gingivitis and experimental mucositis in humans with electromagnetic pulse action.

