3. MATERIAL AND METHODS

3.1. Experimental design

This prospective, controlled study will induce experimental gingivitis and mucositis in humans using the suspension of hygiene of the elements involved in the research: one tooth and 2 implants. The model used will be one in which only the teeth and implants involved in the research will not be cleaned while the entire oral cavity of

the study participant will be cleaned. To this end, the participants will be molded and will receive an acetate plate that will cover the teeth involved in the research, protecting them from the toothbrush. Participants selected for the study must sign the Informed Consent Form (ICF) after verbal and written explanation of the project. Subjects will receive oral hygiene instruction and biweekly professional prophylaxis within 30 days prior to implant placement. The implants will be installed in time -60 days. After 60 days, that is, at time 0, the healers will be installed in the two implants, one being a conventional healer and the other with an electromagnetic pulse. At the same time, everyone will receive acetate plates to protect the selected areas (tooth and implant) during brushing, to be used for 21 days. Periodontal clinical examination, microbiological (supragingival and subgingival biofilm) and immunological (crevicular fluid) collections will be obtained at times 0, 3, 7, 14, 21, 42 and 60 days. The choice between the implant that will receive the conventional healer or the one with electromagnetic pulse will be made randomly, by means of a randomization table. At the end of the study, they will again receive professional prophylaxis and control of oral biofilm after the experiment. Figure 1 shows the study design.

[figure not shown]

Figure 1. Study design.

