4. ETHICAL CONSIDERATIONS

4.1. Description of methods that affect the research subjects

In this study, the impact of electromagnetic pulse and the difference between teeth and implants for oral bacterial biofilm accumulation will be evaluated. Clinical examinations will be performed on all implants and teeth evaluated, as well as collection of submucosal biofilm from the tooth and implant test sites.

4.1.1 – Gengivite e mucosite experimental

Experimental gingivitis has been an efficient, well-documented, and accepted tool in clinical research with different objectives in the last 20 years, as shown in Table 1. There are no reports of any local and/or systemic problems associated with its realization. It is known, however, that a small local and reversible inflammation, compatible with gingivitis (periodontal pathology found in a large part of the world population), can be observed at the end of the biofilm formation period, without permanent damage to the periodontal and peri-implant health of the volunteers and reversed immediately after the resumption of oral hygiene procedures.

Table 1 - Research that has used experimental gingivitis as an analysis methodology in the last 20 years.

Authors	Location, year.	Objective of the Study
McKenna et al.	United Kingdom, 2013	To evaluate the effect of subgingival ozone and/or hydrogen peroxide on the development of periimplant mucositis.
Salvi et al.	Switzerland, 2011	To evaluate the clinical, microbiological, and immunological factors involved in the pathogenesis of gingival inflammation and experimental periimplantation and to compare the sequence of resolution of inflammation around the tooth and implants after restitution of mechanical biofilm removal.

Zitzmann et al.	Switzerland, 2001	To analyze the expression of endothelial cell adhesion in the alveolar mucosa, gingiva, and periimplant mucosa in humans.
Tawse-Smith et al.	Nova Zealand, 2001	To compare the clinical efficacy of manual toothbrush (Oral-B Squish-grip) and electric toothbrush (Braun Oral-B Plaque Remover 3-D) in a group of elderly patients with implant-supported mandibular overdentures.
Zitzmann et al.	Switzerland, 2000	To evaluate soft tissue reactions to biofilm accumulation in teeth and implants.
Pontoriero et al.	Switzerland, 1994.	To compare clinical and microbiological parameters during the development of experimental gingivitis and mucositis, 6 months after implant installation in humans.

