In addition, the study participant will receive verbally and also in writing the Informed Consent Form (ICF; Appendix I: Informed Consent Form) the recommendation to contact the principal investigator in case of the occurrence of any undesirable effect. If necessary, the researcher will make the decision to resume oral brushing in the 3 sites evaluated (2 implants and 1 tooth) and in this case, the participant will be immediately removed from the study, without prejudice to the basic treatment of hygiene or prosthetic restorations of the implants (receiving the crowns/teeth), that is, they will continue to receive this treatment free of charge. Participants will be followed up until the end stipulated by the research. After this period, participants will be instructed to look for the Clinical Studies Center of the Dentistry course at Univeritas-UNG University or specialized centers in Implantology, if they need any assistance. This return protocol will be the same used for other patients in specialization courses.

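### The title, and one reading of the objective, extend the electromagnetic pulse to gingivitis, but only the two implants are randomised to it, so the plan cannot support a conclusion about a pulse effect on gingivitis

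*Combined protocol and SAP*

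**What the plan says.** **Scope.** The title announces modulation by the electromagnetic pulse of the oral "BIOFILM OF INDUCED GINGIVITIS AND MUCOSITIS: PROTEOMIC AND" microbial effects. Section 2 sets the aim of evaluating the host response (proteomic, microbial, clinical) "during induction and progression of gingivitis and experimental mucositis in humans with electromagnetic pulse action", and the abstract repeats it in similar words.

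**Sites.** Section 3.1 induces disease "using the suspension of hygiene of the elements involved in the research: one tooth and 2 implants". Section 4.1.2 also counts three evaluated sites, two implants and one tooth.

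**Allocation.** At time 0, "the healers will be installed in the two implants, one being a conventional healer and the other with an electromagnetic pulse" (Section 3.1). "The choice between the implant that will receive the conventional healer or the one with electromagnetic pulse will be made randomly", from a randomisation table; Section 3.5.1 says the same. Nothing is fitted or allocated to the tooth.

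**Narrower statements elsewhere.** The Introduction gives experimental mucositis as the setting in which PEMF is of interest. Section 4.1 says that "the impact of electromagnetic pulse and the difference between teeth and implants for oral bacterial biofilm accumulation will be evaluated", which reads as two questions.

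**Analysis.** The only group comparison that Section 7 names is gingivitis against mucositis at the different times. The proteomic part of Section 3.6 likewise compares periodontal with peri-implant tissue. Neither names PEMF healer against conventional healer.

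**The concern.** A PEMF effect on gingivitis would have to come from comparing gingival sites with and without the device. The design has no such pair, within or between participants. A report written to the title could still draw that conclusion, and the comparisons most readily at hand would be tooth against PEMF implant, or teeth against all implants. In both, the tissue differs as well as the device. The Introduction itself cites evidence that peri-implant tissue may respond more intensely than gingiva and with different cytokines, so a difference between tooth and implant cannot be credited to PEMF.

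The analysis section adds to the risk. Because it labels groups by disease only, the PEMF and conventional implants fall under one name, mucositis, and the one randomised comparison in the study is never stated.

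**Working it through.** **Inputs.** 40 participants (Sections 3.2 and 3.3); one tooth and two implants each (Section 3.1); one implant of each pair randomised to PEMF (Sections 3.1 and 3.5.1).

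**The plan's own figure.** Section 3.2 gives 40 participants for 85% power. It cannot be reproduced, because no endpoint, effect size, variance, correlation or test is stated. It is not in dispute here.

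**Count.** Sites: 40 × 3 = 120, of which 40 are teeth, 40 conventional implants and 40 PEMF implants. Teeth allocated to PEMF or to control: 0. Randomised implant pairs: 40.

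**What each comparison estimates.** Write t for the mean at an unexposed tooth, τ for the tissue difference (implant minus tooth) and δ for the PEMF effect at an implant. If no field reaches the other sites, the means are t (tooth), t + τ (conventional implant) and t + τ + δ (PEMF implant).

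| Comparison | Estimates |
|---|---|
| PEMF implant − conventional implant | δ |
| Conventional implant − tooth | τ |
| PEMF implant − tooth | τ + δ |
| Mean of both implants − tooth | τ + δ/2 |

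The last line is the gingivitis versus mucositis comparison with the implants pooled: ½(t + τ) + ½(t + τ + δ) − t = τ + δ/2. The first two lines separate device from tissue; the last two do not. None contains a PEMF effect at the tooth.

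**Formal check.** A site-level model with an intercept, tooth, PEMF at implant and PEMF at tooth has 4 columns and rank 3; with participant effects, rank 42 of 43 columns. The missing dimension is PEMF at tooth, whose column is zero in all 120 rows. This result follows from coding the tooth as unexposed, so it restates the allocation and says nothing about stray field.

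**If the field spreads.** Let a be its effect at the conventional implant and b its effect at the tooth. The first comparison becomes δ − a and the second τ + a − b. The quantity b would be a PEMF effect on gingivitis, but it appears only mixed with τ and a.

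**Could distance from the emitter be used?** Section 3.2 requires implants next to teeth in the same hemiarch. If the study tooth adjoins one implant, chance decides whether that implant carries PEMF. Assuming a 20/20 split, two-sided α = 0.05 and 85% power, the standardised difference needed is (1.960 + 1.036) × √(2/20) = 0.95, or 0.97 with the t distribution. For 40 implant pairs it is (1.960 + 1.036)/√40 = 0.47, or 0.49 with the t distribution. The two are on different scales (between-participant SD and SD of paired differences). The documents give no effect size to set against either.

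**The case against.** The strongest reply is that the intent is already narrower than the title. Section 2 is descriptive: it speaks of a response pattern and states no effect or hypothesis, and its closing phrase may attach to mucositis alone or to the experiment as a whole. The Introduction motivates PEMF for mucositis, Section 4.1 lists two questions, and no test in Section 7 is a PEMF contrast on teeth. An unsupported gingivitis claim is therefore a risk in reporting and not a planned analysis. All of this stands. It does not correct the title, and it does not supply the randomised comparison that Section 7 omits.

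A reader might go further and infer that a PEMF effect on gingivitis could not be identified at any sample size, or that the design has no degree of freedom for it. The documents do not support that. It presumes zero exposure at a tooth that may adjoin the emitter, while field reach and the position of the study tooth are not described. A contrast by proximity is conceivable. What can be said is that none is defined or planned.

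Figure 1 is not shown, but the text on sites and allocation is consistent across Sections 3.1, 3.5.1 and 4.1.2.

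**Conclusion.** The point holds as a mismatch between claim and design. The title, and one reading of the objective, cover a PEMF effect on gingivitis; the allocation provides 40 randomised implant pairs and no allocated teeth. A tooth versus PEMF-implant difference carries the whole device effect on top of the tissue difference, and the pooled comparison carries half of it.

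The randomised comparison between the two implants is unaffected. It should not be inferred that the objective asserts a causal effect on gingivitis, since its wording is descriptive.

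The conclusion rests on the tooth receiving no device, which the text supports throughout, and on reading the mucositis group of Section 7 as both implants, which the section neither states nor excludes. The sizes τ + δ and τ + δ/2 also assume no spill-over and equal weight for the two implants.

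**What to change.** Restate the objective, and the comparisons in Section 7, as two aims:

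1. Randomised, paired within participant: PEMF healer versus conventional healer in experimental peri-implant mucositis.
2. Observational, paired within participant: the tooth versus the conventional-healer implant over time. The PEMF implant is left out of this comparison. State that both sites lie in the same hemiarch as the emitter, so spill-over cannot be excluded and neither can be assumed free of PEMF. Exposure of the conventional implant would also shift the first comparison (δ − a above), so the same caveat belongs there.

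Limit statements about PEMF in the title, abstract and conclusions to peri-implant mucositis, and say that no PEMF effect on gingivitis will be claimed.

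The cost is a narrower claim and edits to the title, abstract, objective and Section 7. The 40 participants, the visits and the samples do not change.

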3. MATERIAL AND METHODS

3.1. Experimental design

This prospective, controlled study will induce experimental gingivitis and mucositis in humans using the suspension of hygiene of the elements involved in the research: one tooth and 2 implants. The model used will be one in which only the teeth and implants involved in the research will not be cleaned while the entire oral cavity of

the study participant will be cleaned. To this end, the participants will be molded and will receive an acetate plate that will cover the teeth involved in the research, protecting them from the toothbrush. Participants selected for the study must sign the Informed Consent Form (ICF) after verbal and written explanation of the project. Subjects will receive oral hygiene instruction and biweekly professional prophylaxis within 30 days prior to implant placement. The implants will be installed in time -60 days. After 60 days, that is, at time 0, the healers will be installed in the two implants, one being a conventional healer and the other with an electromagnetic pulse. At the same time, everyone will receive acetate plates to protect the selected areas (tooth and implant) during brushing, to be used for 21 days. Periodontal clinical examination, microbiological (supragingival and subgingival biofilm) and immunological (crevicular fluid) collections will be obtained at times 0, 3, 7, 14, 21, 42 and 60 days. The choice between the implant that will receive the conventional healer or the one with electromagnetic pulse will be made randomly, by means of a randomization table. At the end of the study, they will again receive professional prophylaxis and control of oral biofilm after the experiment. Figure 1 shows the study design.

[figure not shown]

Figure 1. Study design.

